1.1 Background

Cholestasis is a pathological condition in which bile flow from the liver to the gall bladder or intestine is reduced or blocked, leading to accumulation of potentially toxic biliary constituents. PBC is an autoimmune disease of unknown etiology characterized by slowly progressive cholestasis that may lead to cirrhosis, liver transplantation or death. The only approved therapy for PBC is the bile acid ursodeoxycholic acid (UDCA), however this is ineffective in approximately 40% patients, which highlights the need for new drugs.

FXR is a nuclear receptor activated by bile acids ([Chen et al 2004](#); [Makishima et al 1999](#); [Parks et al 1999](#); [Wang et al 1999](#)). When activated, FXR initiates a sensitive, negative feedback loop affecting various aspects of bile acid metabolism resulting in reduced bile acid levels ([Zollner et al 2006](#)). Pharmacological activation of FXR is proposed to be an effective treatment for intrahepatic cholestasis by increasing bile flow from the liver to the intestine, reducing hepatic bile acid uptake and bile acid synthesis, increasing renal bile acid excretion, decreasing circulating bile acid levels and reducing hepatic fibrosis. The therapeutic potential of FXR agonism has been studied in Phase 2 clinical trials and a reduction in biomarkers of cholestatic disease, such as alkaline phosphatase (ALP) and γ -glutamyl transpeptidase (GGT), has been demonstrated ([Mason et al 2010a](#); [Kowdley et al 2011](#); [Hirschfield et al 2015](#)).

LJN452 is a highly potent, specific and orally available FXR agonist. This is a study to determine the safety, tolerability, pharmacokinetics efficacy of LJN452 in patients with PBC.

1.1.1 Relevant data summary

[figure not shown]
Detailed background information on the chemistry, pharmacology, toxicology and pharmacokinetics of LJN452 are given in the Investigator's Brochure. The most relevant data for the present study are summarized in the sections below.

1.1.1.1 Preclinical data

[figure not shown]
[figure not shown]
Pharmacology

In vitro pharmacology studies demonstrate that LJN452 is a potent human FXR agonist with an EC₅₀ of 0.2 nM and 0.3 nM in a cell-based FXR reporter gene assay and in a biochemical co-activator interaction assay, respectively, with >30,000 fold selectivity over other nuclear receptors. Furthermore, LJN452 demonstrated no off-target binding/activity (up to 30 μ M) in a broad specificity-screening panel of receptors, transporters, ion channels, nuclear receptors or enzymes.

FXR agonism has been shown to modify gene expression of a number of enzymes and transporters responsible for drug metabolism and secretion (Calkin and Tontonoz 2012). The time course of effects of LJN452 on the bile salt export pump (BSEP) in preclinical species is detailed in the Investigator's Brochure in addition to potential induction of drug metabolizing enzymes. Drug secretion into bile is typically considered a safe route of clearance. However, biliary delivery of some drugs or their reactive metabolites to the intestinal tract may evoke adverse consequences due to direct toxic actions or indirect disruption of intestinal homeostasis. For example, delivery of reactive metabolites of diclofenac via MRP2 into bile has been linked with NSAID enteropathy (Treinen-Moslen and Kanz 2006).

[figure not shown]

[figure not shown]
In vivo a single oral dose of LJN452 in naïve rats ranging from 0.03-10 mg/kg demonstrated a dose-dependent increase in expression of FXR target genes (liver BSEP and small heterodimer partner (SHP), ileum SHP and FGF15). Dosing of naïve rats with LJN452 (p.o., q.d. for 2 weeks) resulted in modulation of gene expression and clinically relevant pharmacodynamic and biomarker (FGF15) changes at doses as low as 0.01 mg/kg/day.

[figure not shown]

[figure not shown]
Pharmacokinetics

LJN452 has moderate oral bioavailability in animals ($\geq 10\%$). Plasma terminal T1/2 was moderate to long. Clearance and volume distribution were low to moderate. After repeated doses, the exposure was dose proportional with no consistent sex difference. No accumulation was observed in dog, but mild accumulation noted in rat. LJN452 is highly plasma protein bound ($>97\%$). 

1.2 Study purpose

The purpose of Part 1 is to assess the safety, tolerability and efficacy of LJN452 administration for 4 weeks on markers of cholestasis in patients with Primary Biliary Cholangitis (PBC), to enable decisions regarding the further development of LJN452 in the indication of PBC. In addition, data obtained in Part 1 will inform dose selection for Part 2.

The purpose of Part 2 is to further assess the safety and efficacy of two dose levels of LJN452, when administered for longer (12 weeks) and in a wider patient population (both those taking and not taking UDCA). This will provide data to support further development of LJN452 in patients with PBC.

[figure not shown]
2 Study objectives

2.1 Primary objectives

Objective	Endpoint

To determine the effect of LJN452 on cholestatic markers in patients with PBC. More specifically, in Part 2 to determine the dose-response relationship of LJN452 on GGT following 12 weeks of treatment	
Liver function tests, specifically GGT

To determine the safety and tolerability of daily dosing of LJN452 in patients with PBC	
All safety endpoints (including physical exam, vital signs, ECG, safety laboratory tests)Serious adverse events, adverse events

2.2 Secondary objectives

Objective	Endpoint

To evaluate the pharmacokinetics (PK) of LJN452 in patients with PBC	
PK Blood collection

To evaluate the change in overall disease specific quality of life	
PBC40

To determine the change in the itch domain of PBC40 questionnaire	
PBC40

To evaluate the change in itch based on 100 mm visual analog score (VAS)	
Global Itch Visual Analogue Scale

Part 2: To determine the dose-response relationship of LJN452 on ALP in patients with PBC following 12 weeks of treatment	
ALP at baseline and week 13

3 Investigational plan

3.1 Study design

[figure not shown]
This is a randomized, double-blind, placebo-controlled, multi-part study to assess safety, tolerability and efficacy of LJN452 in patients with Primary Biliary Cholangitis (PBC).

Part 1 uses an escalating multiple dose design in PBC patients with incomplete biochemical response to, but still taking, ursodeoxycholic acid (UDCA).

Part 2 is a parallel-group, 12-week study to assess the safety, tolerability and efficacy of two doses of LJN452 compared to placebo in PBC patients with an incomplete biochemical response to, but still taking, UDCA or those not currently taking UDCA. The two LJN452 doses for Part 2 will be selected based on safety, tolerability and efficacy data from Part 1.

Once approximately 40 patients from Part 2 have completed 8 weeks of treatment, an interim analysis will be conducted to re-assess the sample size for Part 2. Recruitment will continue while the interim analysis is performed. [Figure 3-1](#) shows how Parts 1 and 2 are connected.

Figure 3-1 Study design

Part 1

A minimum of 2 and maximum of 5 cohorts of approximately 15 patients with PBC with incomplete biochemical response, but still taking UDCA treatment will be enrolled into Part 1, with the aim of a minimum of 12 patients per cohort completing. Patients withdrawing for reasons other than AEs may be replaced throughout the study. Patients withdrawing from a cohort may not be enrolled in a subsequent cohort.

Figure 3-2 shows the study design of Part 1. At the beginning of Part 1, a screening visit will take place, where a patient's eligibility to enter the study will be assessed. Eligible patients will be admitted to the study site and re-evaluated for inclusion / exclusion criteria during the baseline visit. All baseline safety evaluation results must be available and reviewed prior to first dosing.

Figure 3-2 Study design Part 1

Study Day	1	7	14	21	28	29	56	84
Study visit	↑	↑	↑	↑	↑	↑	↑	↑
Screening	BL	<-	4 week treatment period			->	Follow up	

BL = Baseline assessments

EOS = End of Study visit

↑ = Study visit ↑ = Optional study visit

Patients will be asked to arrive at the study site approximately 2 hours prior to dosing on Day 1. Patients in Cohort 1 will be randomized in a 2:1 ratio to receive the starting dose of 0.03 mg LJN452 or placebo. Safety assessments will be performed for 4 hours post dose and pharmacokinetic [REDACTED] assessments will be performed for up to 8 hours post first dose (see [Assessment schedule](#) for details). Prior to discharge, the patients will be given a supply of LJN452 or placebo and instructed to take first thing in the morning with water, prior to eating every day.

Patients will then return on Days 7, 14 and 21 for safety, pharmacokinetic [REDACTED] assessments and dosing. Patients will be asked to return to the study site on Day 28, for the final dosing visit, when safety, pharmacokinetic [REDACTED] assessments will be performed. Patients will be asked to return to the study site for an optional ambulatory visit on Day 29, where 24 hour post dose pharmacokinetic [REDACTED] assessments will be performed.

Patients are asked to return to the study site on approximately Day 56 for follow up assessments. An end of study visit will take place at approximately Day 84.

A dose escalation review and an interim analysis are planned when at least 12 patients have completed dosing and Day 28 assessments in Cohort 1. The main purpose of the interim analysis will be to evaluate the observed variability in GGT levels and, if needed, consider a sample size re-estimation.

The Lead PI from each active country and Investigators with patients recruited into the cohort will be invited to be involved in the review of blinded data from that cohort and the decision on the dose for the next cohort of subjects (if applicable). Full details of the process are outlined in the Dose Escalation Charter and the SOM.

Additional cohorts will follow the same schedule as Cohort 1. Further cohorts may be added depending on emerging safety and PK/PD data. Additional interim analyses may be performed after a minimum of 12 patients in each cohort finish dosing and Day 28 assessment. The sponsor will be unblinded and the Clinical Trial Team may be unblinded when all subjects in a cohort have completed 28 day of study hence at the time of the planned IAs.

Part 2

Approximately 88 patients with PBC, with an incomplete biochemical response to, but still taking, UDCA or those not currently taking UDCA are planned to be recruited into Part 2, with the aim that 80 will complete the study. Patients who participated in Part 1 may be recruited to Part 2, provided they meet all required eligibility criteria and have not received study medication within 3 months of Randomization, (or longer if required by local regulations) – see exclusion criteria.

Figure 3-3 Study design Part 2

Week	-12 to -2	1	2	3	5	9	13	17
Study visit	↑	↑	TC	↑	↑	↑	↑	↑
Screening		←	-----	12 week treatment period	-----→		Follow up	EOS

BL = Baseline assessments (performed pre-dose Day 1)

↑ = Study visit

TC = Telephone Contact

EOS = End of Study visit

A screening visit will take place, where patient's eligibility to enter the study will be assessed.

Eligible patients will be asked to arrive at the study site approximately 2 hours prior to dosing on Day 1 to perform Baseline assessments.

Patients will be randomized in a 3:3:2 ratio to receive either LJN452 Dose level 1, LJN452 Dose level 2 or placebo. Following drug administration, safety, pharmacokinetic [REDACTED] assessments will be performed at two hours post dose.

Prior to discharge, the patients will be given a supply of LJN452 or placebo and instructed to take their dose first thing in the morning with water, prior to eating every day. New supplies will be dispensed on a monthly basis during regular study visits.

Patients will then return at weeks 3, 5, 9 and 13 for safety, tolerability, pharmacokinetic [REDACTED]. A telephone contact will be made one week after start of dosing to check their progress and check they have no questions.

Patients will be asked to return to the study site in week 17 for follow up assessments and to complete their end of study assessments.

If a patient has a medically important AE that is considered related to study drug and which has not resolved or stabilized at their scheduled end of study visit (week 17), they will be followed, until resolution or stabilization of the AE.

The following will be considered as medically important:

- i) An AE with CTCAE Grade ≥ 3
- ii) SAE
- iii) hepatic and renal events should be followed up per the guidance in [Table 15-1](#) and [Table 16-1](#)

These patients will be monitored by the investigator and have unscheduled visits to collect safety and/or laboratory data. It is advised that the first follow up of these patients with such events will be scheduled at approximately week 21, or sooner based on Investigator's discretion. If events are not resolved or stabilized at this time point, further follow up will be scheduled at the Investigator's discretion and unscheduled visits will be used to collect safety and/or laboratory data. As soon as the event is resolved and/or stabilized, and as long as there are no additional medically important AEs from the treatment period ongoing, no further follow up is required.

3.2 Rationale of study design

This randomized, multi-center, double-blind, placebo-controlled, parallel-group, multi-part study is designed to evaluate safety, tolerability and efficacy of LJN452 (in doses of 0.01 mg and above) relative to placebo in patients with PBC. This will be assessed by a reduction in the cholestatic marker GGT after 4 weeks of double-blind treatment in Part 1 and 12 weeks of double-blind treatment in Part 2.

In Part 1 up to 5 dose levels will be explored to allow characterization of dose exposure response relationship in PBC patients. Randomization in Part 1 has been chosen on a 2:1 ratio in order to rapidly obtain safety and PK data for LJN452. Since 2 cohorts are initially anticipated, the chosen ratio will provide a similar number of patients treated at each dose level to compare with placebo.

In Part 2 two dose levels of LJN452 will be selected based on the safety, tolerability and efficacy data from Part 1.

Randomization in Part 2 has been chosen on a 3:3:2 ratio to enable more safety data to be obtained from patients receiving LJN452. Thus assessment of the safety, tolerability and efficacy of 12 weeks treatment with two dose levels of LJN452 will be assessed, to provide data to support dose selection for future development. In addition, an interim analysis is planned in Part 2 to determine the effect of LJN452 on GGT and itch parameters and to assess the variability for sample size re-estimation, if needed.

In order to maintain the scientific integrity of the study, the investigator and patient will remain blinded to their treatment assignment until database lock (either at the end of the study, or earlier in the event of a staggered lock of Part 1 or cohorts in Part 1).

[figure not shown]
The use of multiple cohorts of ascending dose in Part 1 will allow evaluation of safety, PD and PK starting at a dose below the maximum dose tested so far in healthy volunteers. The multiple cohort dose escalation design will allow characterization of the dose-exposure-response relationship in PBC patients. Escalation will depend on safety parameters and the increment in dose will not exceed 1.67 fold at doses greater than 0.09 mg.

[figure not shown]
Part 1 will provide safety and efficacy data for LJN452 in a population who have not had satisfactory biochemical response to the first line standard of care UDCA and hence are at increased risk of disease progression to hepatic decompensation, transplantation or death. Data obtained in Part 1 will allow selection of doses to be used in Part 2.

Part 2 will provide safety and efficacy data from a longer treatment duration with LJN452 in the same population as well as widening the population to include patients who are not currently taking standard of care, UDCA (patients will be stratified across the treatment groups based on their UDCA status). This group has a high unmet clinical need and is likely to make up a significant minority population in later phase studies.

Patients will also be stratified across the treatment groups based on the severity of any pruritus. Patients with a PBC-40 score at screening of <7 will be classed as low severity and those with a score ≥ 7 will be classed as high severity.

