6.3 Treatment assignment

Randomization numbers will be assigned in ascending, sequential order to eligible subjects (see Site Operations Manual for details).

The randomization numbers will be generated using the following procedure to ensure that treatment assignment is unbiased and concealed from subjects and investigator staff.

In Part 1 a randomization list will be produced by or under the responsibility of Novartis Drug Supply Management using a validated system that automates the random assignment of treatment arms to randomization numbers in the specified ratio. The investigator will enter the randomization number on the CRF.

In Part 2 a subject randomization list will be produced by the IRT provider or by a delegate under their supervision, using a validated system that automates the random assignment of treatments to randomization numbers. These randomization numbers are linked to the different treatment arms.

In Part 2 randomization will be stratified by whether the patient is taking UDCA or not and the severity of pruritus.

Patients who participated in Part 1 may be enrolled in Part 2, provided they meet all the eligibility criteria. They will be assigned a new screening and randomization number. The screening number a subject had in Part 1 will be recorded as part of the CRF data collected for Part 2, if a subject participates in both parts.

The randomization scheme for all subjects will be reviewed and approved by a member of the Randomization Office.

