8.3.2 Patient-Reported Outcome

PBC 40

The PBC-40 is a paper-based patient-derived, disease specific quality of life patient reported outcome (PRO) measure. It was developed and validated for use in subjects suffering from PBC ([Jacoby et al 2005](#)). It is designed for self-completion and takes approximately 5 minutes to complete. It consists of 40 questions arranged in 8 domains with between 3 and 11 questions in each domain. Each question is scored from 1 to 5 in increasing order of severity. The difference in total sum score between each treated group and placebo at Day 28 will be investigated.

PBC40 itch domain

The domain specifically relates to cholestatic itch symptomatology. In addition to the investigation of the total PBC-40 sum score, the sum scores from the 3 question itch sub-domain of the PBC40 questionnaire will be determined and used to test for an effect of LJN452 relative to placebo.

VAS for Itch and Sleep

The Global Itch Visual Analogue Scale, a 100 mm visual analogue scale (VAS) will be used to assess the severity of patients itch (ranging from 0 = none at all to 10 = the worst imaginable itch) and the Sleep Disturbance Visual Analogue Scale will be used to assess the impact of nocturnal itch on sleep (from 0 = no sleep loss to 10 = cannot sleep at all). The score (distance from left) on the VAS will be recorded for both parameters by the patient marking with a line and used to test for an effect of LJN452 over placebo.

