11.5 Analysis of secondary [REDACTED] variables

11.5.1 Efficacy / Pharmacodynamics

The secondary efficacy/PD variables are the PBC-40 total score, the PBC-40 itch domain subscore, and the VAS scale PRO as well as ALP.

The difference between LJN452 and placebo will be assessed by Wilcoxon rank sum test for change from baseline in total PBC score and itch subdomain score at each visit. A two-sided p-value for a treatment difference will be reported with no adjustment for multiplicity. In addition, summary statistics (mean median std min max) will be reported at each applicable time point.

As an additional secondary end point, a 100 mm visual analogue scale (VAS) will be used to assess the severity of patients itch as well as loss of sleep. The score (distance from left) on the VAS will be recorded for both parameters by the patient marking with a line. The distance marked will be converted to a score between 0 and 10.

The change from baseline VAS scores for itch and sleep loss will be analyzed by analysis of covariance with a baseline covariate, a fixed effect for treatment, visit, and treatment by visit interaction as well as visit by baseline interaction. An unstructured covariance matrix will be used 90% two-sided confidence intervals for the difference between each LJN452 dose and placebo will be presented. The UDCA and pruritus stratification factor will also be included as a fixed effect in the model for Part 2 analysis.

ALP data will be analyzed using the same approach as described in [Section 11.4.2](#). Additionally the number and percentage of subjects who have $ALP < 1.67 \times ULN$ with $> 15\%$ reduction from baseline and a normal total bilirubin level will be tabulated by part, treatment and visit.

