#### **7.1.3 Statistical model, assumptions and hypotheses**

Log-transformed changes from baseline for serum GGT will be analyzed by repeated measures analysis of covariance (ANCOVA) for each Part 1 and Part 2 separately. The model will include

treatment as a fixed effect, time as a repeated effect, the treatment by time interaction, the time by log-transformed baseline interaction and log-transformed baseline as a continuous covariate. The UDCA and pruritus stratification factor will also be included as a fixed effect in the ANCOVA model for the Part 2 analysis. A saturated covariance structure will be used for observations within the same subject. The model will be fitted using SAS Proc Mixed and the restricted maximum likelihood scoring method (reml). Two-sided 90% confidence intervals for the difference between each LJN452 dose and placebo will be evaluated for each visit. This will then be “back-transformed” to the original scale to give a fold change from baseline. Dose response may be assessed using appropriate contrasts. The analysis at the Day 28 (Visit 7) and day 85 (Visit 7) will constitute the primary analysis for Part 1 and Part 2, respectively.

The analysis will be done for each study cohort using pooled placebo data within Parts 1 and 2, respectively. No adjustment for multiplicity will be done.

Additionally an exploratory analysis on the combined data from Part 1 and Part 2 may be performed using a similar approach and the correlation between measurements taken in Part 1 and Part 2 from the same subject will be accounted for as appropriate.

Similar analysis as mentioned above can be performed for key LFT parameters.

In Part 2, there is the option of reducing the dose level for the individual subject. If for any subject the dose is reduced during the study, any data after the dose reduction will be set to missing. A repeated measures ANCOVA treating all measurements obtained post dose reduction as missing will be performed as well for Part 2 only.

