### **7.2.3 Statistical model, assumptions and hypotheses**

The difference between each LJN452 dose and placebo will be assessed by Wilcoxon rank sum test for change from baseline in total PBC score and itch subdomain subscore at each visit. A two-sided p-value and 90% CI for each treatment difference will be reported with no adjustment for multiplicity. In addition, summary statistics (mean, median, SD, minimum, maximum) will be reported at each applicable time point.

As an additional secondary end point, a 100mm visual analogue scale (VAS) will be used to assess the severity of patients' itch as well as loss of sleep. The score (distance from left) on the VAS will be recorded for both parameters by the patient marking with a line. The distance marked will be converted to a score between 0 and 10.

The change from baseline in VAS scores for itch and sleep loss will be analyzed by repeated measures analysis of covariance. The model will include treatment as a fixed effect, time as a repeated effect, the treatment by time interaction, the visit by baseline interaction and baseline as a continuous covariate. An unstructured covariance matrix will be used. Two-sided 90% confidence intervals for the difference between each LJN452 dose and placebo will be presented for each visit. The UDCA and pruritus stratification factor will also be included as a fixed effect in the model for the Part 2 analysis. Missing values will not be imputed.

ALP data will be analyzed using the same approach as described in Section 7.1.3.

Additionally, the number and percentage of subjects who have  $ALP < 1.67 \times ULN$  with  $> 15\%$  reduction from baseline and a normal total bilirubin level will be tabulated by part, treatment and visit.

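### Does the Part 2 pruritus stratum fail because the protocol does not say which PBC-40 score is cut at 7?

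*Protocol*

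**What the plan says.** Protocol 3.2 says that Part 2 patients are stratified by how severe their pruritus is and gives the rule in the next sentence: "Patients with a PBC-40 score at screening of <7 will be classed as low severity". A score of 7 or more is high severity. No other place in the protocol or SAP gives a score or a cut.

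Protocol 6.3 names the two factors only: "In Part 2 randomization will be stratified by whether the patient is taking UDCA or not and the severity of pruritus". SAP 7.1.3 carries them into the primary model: "The UDCA and pruritus stratification factor will also be included as a fixed effect in the ANCOVA model for the Part 2 analysis". The same factor enters the ALP and VAS models through SAP 7.2.3.

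Protocol 8.3.2 describes the questionnaire: "It consists of 40 questions arranged in 8 domains with between 3 and 11 questions in each domain". On scoring it says "Each question is scored from 1 to 5 in increasing order of severity". It treats the itch domain separately: "the sum scores from the 3 question itch sub-domain of the PBC40 questionnaire will be determined". Protocol 11.5.1 and SAP 7.2.1 list the total and the itch subscore as two different secondary variables. Table 8-2 schedules the PBC-40 at screening, so both scores would be available when a patient is stratified.

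**The concern.** A stratification rule should be readable without inference, because it has to be programmed before the first patient is randomised and derived again for analysis. Here two scores from the same questionnaire are in play and the rule does not say which one is cut. Someone who takes the unqualified name to mean the whole instrument finds a rule that cannot work, since no 40-item total can fall below 7.

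If it were programmed that way, every patient would be high severity. Stratification would reduce to UDCA use alone, and the pruritus part of the model factor would be constant. Planned balance on baseline itch would be lost in a trial whose Part 2 interim analysis exists to check precision for itch. The PBC-40 comparisons look most exposed, because they use a "Wilcoxon rank sum test for change from baseline in total PBC score and itch subdomain subscore at each visit", with no covariate or stratum to absorb an imbalance.

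**Working it through.** **Inputs** (Protocol 8.3.2 and 3.2): 40 items in total; 3 items in the itch domain; 3 to 11 items per domain; each item scored 1 to 5; cut at 7. The plan states no score range to reproduce.

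**Range of a sum of k items:** minimum k × 1, maximum k × 5.

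| Reading of the score | Range | Below 7 | 7 or above |
|---|---|---|---|
| 40-item total | 40 × 1 = 40 to 40 × 5 = 200 | none | all |
| Mean per item | 1 to 5 | all | none |
| 3-item itch sum | 3 × 1 = 3 to 3 × 5 = 15 | 3, 4, 5, 6 | 7 to 15 |

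On the itch sum there are 15 − 3 + 1 = 13 possible values, 4 low and 9 high. A sum of 6 is an average of 6/3 = 2 per item, so the cut separates patients averaging 2 or less on the five-point item scale from the rest. That is a natural place to divide mild from more marked itch.

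**Is the itch sum the only domain on which 7 could work?** Not by arithmetic. A k-item domain can score below 7 whenever k < 7, so any domain of 3, 4, 5 or 6 items qualifies. Range alone does not settle the reading; subject matter does. The stratum concerns pruritus, and the itch domain is the one that Protocol 8.3.2 ties to itch.

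**Do the documents use the bare name for the total elsewhere?** Where the 40-item sum is meant, it is labelled as a total: in Protocol 8.3.2 (total sum score), Protocol 11.5.1 and SAP 7.2.1 (PBC-40 total score). The rule in Protocol 3.2 has no such label. Reading it as the total adds a word that the text does not contain.

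**What would happen on the unintended reading?** With two levels each, UDCA and pruritus give 2 × 2 = 4 strata. With pruritus constant, 2 remain, defined by UDCA. A constant term is absorbed by the intercept, so the GGT and ALP models would keep treatment, visit, log baseline, their interactions and UDCA. The VAS model would keep its own baseline covariate. Randomisation would still be random, so treatment differences would remain valid; only planned balance on itch would be lost.

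**The case for a change.** The strongest reply is that evident intent is not a specification. The person who sets up the randomisation system and the person who derives the factor for analysis both have to infer the variable from context, and in principle could infer differently. The SAP, where a derivation would normally be found, gives neither score nor cut. Naming the domain would take one phrase.

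It stands that the label is missing from the one visible place where the cut is given. The consequence does not follow. For the two people to diverge, one would have to choose a score on which one stratum is empty, or a domain unrelated to pruritus. An empty stratum would be hard to miss at set-up, though that is a judgement and not something the documents show. The visible documents are also not the whole specification: Protocol 6.1.1 sends the reader to the Site Operations Manual and the randomisation system's user manual, and SAP 1.1 assigns derived-variable specifications to Module 8.

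The point about the unstratified Wilcoxon tests is a separate analysis choice. It would be the same whichever score defines the stratum, so it adds no weight here. A figure for chance imbalance in itch would need a prevalence that the documents do not give, and it would describe randomisation without an itch stratum, which nothing in the text indicates.

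**Conclusion.** The concern does not hold as a defect in the plan. The rule lacks a domain label, but its context, the documents' own naming of the total and the score ranges all lead to the 3-item itch sum, with 3-6 low and 7-15 high. An analyst or programmer would fill this gap sensibly. No sample size, power figure, estimate or decision rule changes when it is filled. Even on the unintended reading the treatment comparisons would remain valid, and the loss would be planned balance on one baseline factor.

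This rests on the item counts and scoring in Protocol 8.3.2, and on the assumption that the randomisation system was set up on the itch sum. That set-up cannot be checked from the protocol and SAP, but nothing in them suggests that another score was used.
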